The primary outcome in this study will be change in VE/VCO₂ slope. The VO₂ change outcomes will be assessed for normality using standard visual assessments (Q-Q plots and histograms) and statistical tests (Kolmogorov-Smirnov). If VE/VCO₂ slope change demonstrates evidence for non-normality, we will natural log transform values for our primary analyses. Prior to testing for differences, we will compare important clinical, laboratory and demographic characteristics between groups (treatment vs. control) to ensure that randomization achieved between groups balance on these important covariates. For variables that are unbalanced by treatment group (determined via statistically significant difference $p<0.05$), we will include these variables in multivariable models of the primary endpoint as described below. Linear regression models will be used to regress mean weight change on treatment group using intention-to-treat principles. If preliminary descriptive analyses indicate a need for multivariable models (see above), the relevant adjustments will be made to our regression models. Analysis of secondary outcomes will be conducted using contingency tables and Fisher's exact chi-square tests; for these outcomes, we will also utilize a modified Poisson regression model with robust error variance to assess the relative risk (separate regressions for each outcome). This modified Poisson model has been described previously and allows for multivariable models to be constructed should they be deemed necessary. Once a patient is randomized, they will be included in final analyses according to intention-to-treat principles regardless of whether they complete the study protocol. If patients are lost-to-follow up and final outcome assessments cannot be made we will use the "last observation carried forward" approach to assign a final outcome value. Additional sensitivity analyses will be performed by assigning final outcome values assuming patients in the treatment group had 10% lower mean weight loss and patients in the control group had 10% greater mean weight loss. This is very conservative approach that will inform the potential for differential outcomes according to follow-up status to explain our observed findings. However, we expect very little loss-to-follow up as these patients receive regular care at our center and are likely to return to the hospital regardless of continued study participation.

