Power for VE/VCO₂: We base the sample size calculation on data from Wong et al (31). We estimate the average effect size of metformin on the slope of VE/VCO₂ to be -5 with a starting average slope of 32 and a variance of 6. In order to achieve 83% power with an alpha of 0.05, we will enroll 25 patients in each arm.

Positron Emission Tomography (PET) Sub-study (IRB AAAR 9360)

The goal of this sub-study is to enroll patients to undergo cardiac PET imaging before and after treatment with either metformin or placebo. In this pilot sub-study, we will recruit patients at the time of their enrollment into Met-HeFT to undergo serial PET scans with metabolic tracers. We will specifically use FDA approved radiotracers for this study including ¹⁸F-Fluorodeoxyglucose (¹⁸F-FDG) to track myocardial glucose consumption and ¹³N-ammonia (¹³N-NH₃) to track perfusion. With these combination of radiotracers, we will be able to quantitatively measure myocardial metabolism and its reliance on different pathways that may be influenced by metformin.

Consecutive patients in Met-HeFT will be recruited at the time they are enrolled in the trial to be included in the sub-study. The decision to enroll in this sub-study will have no effect on their enrollment in Met-HeFT. After enrollment, patients will undergo a PET scan using two radiotracers: ¹⁸F-FDG and ¹³N-ammonia. Scans will occur prior to initiation of the study drug and at the 6 month end of study mark. Patient randomization will be maintained and both the study participants, coordinators and investigators will be blinded to patient assignment.

Inclusion/Exclusion Criteria: Any patient enrolled and meeting all inclusion criteria for Met-HeFT will be eligible to elect for inclusion into this sub-study.

Pregnancy Test: Women of childbearing potential will provide a urine specimen to determine if they are pregnant. Pregnant women will be excluded from the study. The source of the urine specimen will be from Columbia and/or NYPH Subjects/Patients or repositories managed by Columbia. The specimen will be labeled with direct identifiers.

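### The fallback for the primary analysis, read naturally, logs the change in VE/VCO₂ slope, and that log does not exist for any change at or below zero

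*Combined protocol and SAP*

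**What the plan says.** The Statistical Approach section opens: "The primary outcome in this study will be change in VE/VCO₂ slope". It then sets a conditional rule. Should that change look non-normal, the plan says "we will natural log transform values for our primary analyses". Non-normality is to be judged from Q-Q plots, histograms and a Kolmogorov-Smirnov test, with no stated criterion for when these count as evidence. The sentence that introduces those checks names VO₂ change, not VE/VCO₂ slope change, as the variable examined.

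The section mentions no offset, no ratio of final to baseline, and no rank-based alternative. It promises that every randomized patient enters the final analysis under intention-to-treat, and it fills missing final outcomes by last observation carried forward.

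The paragraph on power for VE/VCO₂ gives the expected size and sign: "We estimate the average effect size of metformin on the slope of VE/VCO₂ to be -5". The spread is given beside the baseline mean, in the words "with a starting average slope of 32 and a variance of 6". The target is 83% power at alpha 0.05, and for this the plan states "we will enroll 25 patients in each arm".

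**The concern.** The only variable named in the conditional sentence is the slope change, so an analyst following it would log the changes. With change taken as final minus baseline, which the -5 implies, every patient who improves has a negative value and the log cannot be computed.

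The analyst would then have to do something the plan does not describe. Leaving those patients out would select on the outcome, remove more patients from the metformin arm than from placebo if metformin works as planned, and break the intention-to-treat commitment. Adding a constant to make all values positive would mean choosing that constant after the outcomes are known. Either way, the result for the single primary endpoint of a 50-patient trial would rest on an unplanned decision.

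**Working it through.** **Inputs.** From the power paragraph: effect -5, spread 6 (printed as a variance), alpha 0.05, 25 patients per arm, 83% power. From the CPET paragraph and Table 1: exercise tests at baseline and the final visit only. Assumed here, because the documents do not say: normally distributed changes, the planning spread applied to the change, and a mean placebo change of 0, varied below.

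**1. Which spread the plan used.** Two-sided power for two means is approximately Φ(|δ| / (SD·√(2/n)) − 1.96).

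- SD 6: 5 / (6·√(2/25)) = 5 / 1.697 = 2.946, and Φ(2.946 − 1.960) = Φ(0.986) = 83.8%. The exact noncentral t value is 82.3%. Both agree with the stated 83%.
- Literal variance 6, so SD = √6 = 2.45: 5 / 0.693 = 7.2, and power is practically 100%.

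The plan's figure is reproduced by SD 6, so that is the main case. The literal variance is carried as a sensitivity case.

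**2. Share of patients with a negative change.** With mean placebo change p, the metformin mean is p − 5. The shares are Φ((5 − p)/SD) on metformin and Φ(−p/SD) on placebo, averaged 1:1.

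| SD | p | Metformin | Placebo | Overall |
|---|---|---|---|---|
| 6 | 0 | 79.8% | 50.0% | 64.9% |
| 6 | -1 | 84.1% | 56.6% | 70.4% |
| 6 | +1 | 74.8% | 43.4% | 59.1% |
| 2.45 | 0 | 97.9% | 50.0% | 74.0% |
| 2.45 | -1 | 99.3% | 65.8% | 82.6% |
| 2.45 | +1 | 94.9% | 34.2% | 64.5% |
| 4 | 0 | 89.4% | 50.0% | 69.7% |
| 8 | 0 | 73.4% | 50.0% | 61.7% |

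In the main case, 25 × (0.798 + 0.500) = 32.4 of 50 patients have no defined log. About 5 metformin and 12 to 13 placebo patients remain.

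**3. Carried-forward values.** The only exercise test before the final visit is the baseline test. Carrying it forward makes final equal to baseline and the change exactly 0. Log 0 is undefined whichever way change is signed.

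**4. Opposite sign.** If change is coded as baseline minus final, the undefined patients are those who worsen: 100% − 64.9% = 35.1% in the main case.

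**5. Log of the slopes themselves.** At means 32 and 27 with SD 6, the chance of a slope at or below zero is Φ(−32/6) ≈ 0.00000005 and Φ(−27/6) ≈ 0.000003. On this scale the problem disappears.

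**The case against.** The strongest reply is that 'values' carries no qualifier. The authors may have meant the measured slopes, which are all positive, and step 5 shows that the rule would then work. This reading cannot be excluded, but the text does not state it: the outcome and the trigger are both the change. Two analysts could follow the sentence and run different primary analyses, so it needs correction on either reading.

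The other objections limit the size of the point:

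- SD 6 is inferred from the power figure, and a placebo change of 0 is assumed. The shares also come from a normal model, while the rule applies only when normality is doubted. They are illustrations.
- The direction of subtraction is never defined. The -5 points to final minus baseline. The opposite coding reduces the loss but does not remove it.
- The rule is conditional. A reader might infer that the primary analysis is bound to fail, or that two thirds of the patients will be lost. The documents do not support this: without the trigger nothing is logged, and they give no basis for the probability that it fires.
- A reader might argue from the properties of the Kolmogorov-Smirnov test that the rule would hardly ever fire. That does not settle the matter, because the plots are triggers too and the behaviour of one test is not that of the whole gate.
- A reader might try to calculate the biased treatment effect left after deleting undefined patients. The plan does not say that they would be deleted, and its intention-to-treat commitment points the other way, so no such estimate can be attributed to it.

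**Conclusion.** The point stands as a defect in a conditional rule for the primary endpoint. Taken in its natural sense, the rule cannot be carried out for any patient whose change is zero or below, and it conflicts with the promise to analyse everyone randomized. Under the main assumptions about 65% of patients are affected. In every case in the table the share exceeds half: 59% to 70% at SD 6 and about 64% to 83% at the literal variance, for mean placebo changes from -1 to +1. With change coded as a reduction it is about 35%. The exact share depends on those assumptions. The conclusion needs only that some patients have a change at or below zero, which the planned effect and the carry-forward rule make practically certain. An untransformed analysis is unaffected.

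**What to change.** Delete the normality-triggered log rule. State instead that the day-180 VE/VCO₂ slope will be analysed on its original scale by linear regression on treatment, with baseline slope as covariate. With baseline in the model, the treatment coefficient is the same whether the response is the final slope or the change, so the stated endpoint is kept and the sign convention no longer matters.

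If a log scale is wanted, specify it in advance: log the day-180 slope and adjust for the log of the baseline slope. Both are positive. Never log their difference.

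In the same section, correct the sentence on VO₂ change so that it names the VE/VCO₂ slope. A permutation test of the treatment effect can be added as an optional sensitivity analysis for those worried about non-normality.

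The cost is a wording change in the Statistical Approach section, best made before outcomes are examined by arm. No new data, visits or patients are needed.

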- Planned major surgery within the study period
- Female patients who are pregnant, nursing, or of childbearing potential while not practicing effective chemical contraceptive methods (i.e. oral, implanted, injectable, or transdermal contraceptive hormones; intrauterine device)
- Current abuse of alcohol or drugs
- Life-expectancy of less than 1 year due to co-existing morbid illness
- Liver disease with ALT or AST >3 times upper normal limit (it is possible to repeat this measurement once within a month)
- Advanced lung disease such as COPD
- Significant comorbidity or issue that makes the patient unsuitable for participation as judged by the investigator

- Participation in another study involving long-term medical intervention (participation in device studies is allowed)

Randomization: After obtaining informed consent, subjects who meet all the inclusion criteria and none of the exclusion criteria will be randomized. Patients will be randomly assigned in a 1:1 ratio to metformin (1000mg twice a day) or placebo treatment groups. The randomization code will be generated by the Columbia University Irving Institution Biostatistics Epidemiology and Research Design Resource (BERD) and held by the Columbia University Medical Center (CUMC) research pharmacy in opaque envelopes prior to the initiation of patient recruitment to ensure allocation concealment. The study drug will be dispensed by the research pharmacy based on randomization assignment. Principal investigator/Co-investigators are responsible to assess the eligibility criteria. Patients and physicians will be blinded to the intervention allocation. Randomization will be performed in block permutations designed by BERD in order to balance the issue of maintaining similarity between treatment groups while simultaneously not employing block sizes which are so small that it is possible to guess some allocations, thus reducing blinding in the trial. A separate randomization table will be generated for those subjects who agree to the PET sub-study (IRB AAR9360). The goal of having two tables is to maintain balanced enrollment between those that do and do not agree to participate in the PET sub-study.

Study Intervention and Procedures

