Cardiopulmonary Exercise Test (CPET): At baseline and final visit. The CPET is to be performed on a either a treadmill with a Medgraphics Ultima metabolic cart or a Corival CPET Ergometer (stationary bicycle) in the Cardiopulmonary Exercise Lab. All testing is to be done in the Cardiopulmonary Exercise Lab in Milstein, a clinical cardiopulmonary exercise testing laboratory. There will be a physician present at all tests, and the appropriate emergency equipment and trained personnel are available should difficulties arise during the exercise test. The CPET will be conducted per ATS and AHA guidelines (25, 26). For a treadmill test: Participants will exercise on a treadmill at an increasing rate of 0.1MPH per minute and 1% grade per minute starting at a speed of 1.0 MPH at 0% grade. For a bicycle test: The participants will perform a 15 watt ramp protocol and instructed to pedal to a rate of 50-60 rpm. The protocol begins at zero watts and will increase in resistance by either 15 watts/minute (for female patients) or 20 watts/minute (for male patients) Heart rate, BP and perceived exertion score (RPE, reported on a scale from 0-10.0) will be recorded in one-minute intervals. Oxygen consumption (VO2) (ml/min), Carbon Dioxide production (VCO2) (ml/min), and minute Ventilation (VE) (L/min) will be measured on a

breath by breath basis. Peak VO₂, VE/VCO₂ and respiratory exchange ratio (RER) will be computed.

Biobank: Serum samples will be stored in a biobank repository in the CCTI Biobank Core Facility. The purpose of this biobank is to characterize serum biomarkers of patients with heart failure who have been exposed to metformin versus placebo. The registry will include previously gathered clinical information in electronic medical records. This data includes demographics, clinical comorbidities, hemodynamics, echocardiographic indices of structure and function, hospitalizations, medication use and laboratory data. All specimens/data will be distributed at the discretion of the principal investigator. The purpose of this dissemination will be for experimental collaboration. We will review to make sure collaborators have an existing approved IRB before we distribute. The proper MTA will be executed prior to delivery of samples. All samples will be coded so the recipient will not have any direct patient identifiers linked to these samples.

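### The primary model adds covariates only after a baseline p<0.05 test, which omits the baseline VE/VCO₂ slope in about 95% of trials, and its defining sentence names the wrong outcome

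*Combined protocol and SAP*

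**What the plan says.** The Statistical Approach section opens by making change in VE/VCO₂ slope the primary outcome. Covariates are then chosen from the data: "For variables that are unbalanced by treatment group (determined via statistically significant difference $p<0.05$), we will include these variables in multivariable models". The variables to be compared are described only by type. None is named, and the baseline slope is not mentioned.

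The sentence that defines the model reads: "Linear regression models will be used to regress mean weight change on treatment group using intention-to-treat principles". The normality check begins with a different quantity: "The VO₂ change outcomes will be assessed for normality using standard visual assessments". The sensitivity analysis for missing outcomes is framed as "assuming patients in the treatment group had 10% lower mean weight loss". Under Endpoints, body weight and peak VO₂ are secondary, and the Primary Endpoint Rationale explains why peak VO₂ was not made primary.

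On transformation the plan says: "If VE/VCO₂ slope change demonstrates evidence for non-normality, we will natural log transform values for our primary analyses". It names visual checks and a Kolmogorov-Smirnov test but gives no threshold.

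Two design facts bear on the model. The baseline slope will be available: "Cardiopulmonary Exercise Test (CPET): At baseline and final visit", repeated in Table 1. Randomisation is also split by sub-study participation: "A separate randomization table will be generated for those subjects who agree to the PET sub-study".

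**The concern.** In a randomised trial, a baseline difference at p<0.05 arises by chance. It does not show that the variable predicts the outcome, which is the reason to adjust. The rule therefore leaves out a strong candidate covariate, the baseline value of the outcome, in nearly every trial. It may also bring in variables of no prognostic value.

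Because the list is open, the covariates in the primary model cannot be stated before the data are seen. No sentence gives a regression with change in VE/VCO₂ slope as the dependent variable.

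The log rule has two faults. Its subject is the change, and a negative change has no log; the planned effect is itself -5. If the visit slopes are meant instead, a check without a threshold can switch the primary result from a difference to a ratio.

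PET participation is in effect a stratification factor. Blocks within each table keep it balanced between arms, so a test for imbalance will hardly ever select it.

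What is at stake is precision in a 50-patient trial and a primary analysis that can be verified as pre-specified.

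**Working it through.** **Inputs.** From Power for VE/VCO₂: difference -5, a spread of 6, 25 per arm, alpha 0.05 (taken as two-sided), stated power 83%. Not in the documents, so assumed: baseline-final correlation r = 0.5, 0.7 or 0.9, with equal variance at both visits. All calculations take 50 complete patients.

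**The plan's own figure.** Read as an SD, 6 gives SE = 6 × √(2/25) = 1.697. Power is 83.8% by the normal formula and 82.3% by the t test (48 df). Read as a variance, as the text has it, the SD is √6 = 2.449 and power exceeds 99.9%. Only the SD reading comes near 83%, so it is used below.

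**How often the baseline slope enters.** Under randomisation a test at 0.05 is significant in 5% of trials. Simulation (20,000 trials per scenario, assumed blocks of 4 within each PET table, half the patients in PET) flagged it in 4.9%, 5.1% and 4.9%. If the slope is not among the variables tested, it never enters.

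**Chance flags among other variables.** With 10 or 20 independent variables tested (numbers assumed), the probability of at least one flag is 1 - 0.95^10 = 40% or 1 - 0.95^20 = 64%.

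**Precision, with 6 as the SD of change.** Visit SD = 6/√(2(1-r)) = 6.00, 7.75, 13.42. Residual SD given baseline = visit SD × √(1-r²). With baseline slope and PET participation in the model there are 46 df, and SE = residual SD × √(2/25) × √(1+1/46).

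| r | Residual SD | SE | Power, unadjusted | Power, p<0.05 rule (simulated, applied to baseline slope) | Power, pre-specified | Unadjusted n per arm to match |
|---|---|---|---|---|---|---|
| 0.5 | 5.20 | 1.486 | 82.3% | 83.6% | 90.9% | 33 |
| 0.7 | 5.53 | 1.582 | 82.3% | 83.0% | 87.2% | 29 |
| 0.9 | 5.85 | 1.672 | 82.3% | 82.4% | 83.3% | 26 |

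Simulated power for the pre-specified model was 91.2%, 87.0% and 83.4%. A separate simulation adjusting for baseline slope alone (60,000 trials per setting) gave 90.7%, 87.4% and 83.3%, against 83.0%, 82.9% and 82.3% under the rule.

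**Precision, with 6 as the SD at each visit.** SD of change = 6 × √(2(1-r)) = 6.00, 4.65, 2.68. Power, unadjusted then pre-specified, is 82.3% and 90.9% at r = 0.5, 96.1% and 97.9% at r = 0.7, and above 99.9% for both at r = 0.9.

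**Bias and type I error.** The mean simulated estimate was -5.0 throughout. Under the null, the p<0.05 rule rejected in 4.5%, 4.5% and 4.7% of trials and the pre-specified model in 5.1%, 5.0% and 4.8%.

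**PET participation.** With PET patients differing by 3 or 6 units at both visits (r = 0.7), the unadjusted type I error was 4.8% and 5.2%. A difference present at both visits cancels in the change.

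**The case against.** The size of the loss rests wholly on an assumed correlation. At r = 0.9 the gain is about 1 point, and if 6 is the spread at a visit there is little to gain above r = 0.5. The outcome is already a change score, so baseline is not ignored; what is forgone is the further gain from covariate adjustment. Unadjusted power of 82% is essentially the planned 83%, so the rule does not take the trial below its target. All of this stands, and it limits the point to precision and pre-specification.

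The 40% and 64% figures assume independent variables; positively correlated ones would be flagged somewhat less often. The simulated rule tests only the baseline slope, whereas the plan's rule covers an unlisted set.

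The PET term explains almost none of the gain, as the baseline-only simulation shows. The case for it is that the analysis should match the randomisation.

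The weight wording looks clerical, since the protocol elsewhere names VE/VCO₂ as primary and the covariate sentence refers to the primary endpoint. Probably so, and the default treatment-only structure is stated. As written, though, the dependent variable is wrong and no other passage supplies the right one.

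**Conclusion.** The concern holds. The covariate rule selects on chance imbalance, omits the baseline slope in about 95% of trials (always, if it is not tested) and leaves the covariates undefined until the data are seen. The outcome is misnamed in three sentences, and the log rule cannot be applied to a negative change.

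The estimate is unbiased over randomisations and overall type I error is not inflated. With 6 as the SD of change, always adjusting raises power over the unadjusted analysis by about 9, 5 and 1 points at r = 0.5, 0.7 and 0.9, and lowers the SE from 1.70 to 1.49, 1.58 and 1.67. These sizes depend on the assumed r and on the reading of 6. The wording defects do not, and need correcting whatever the correlation. Leaving out PET participation would affect error rates only if it predicts change in slope, which the documents do not show. The change should be made, but the planned power does not depend on it.

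**What to change.** Amend the Statistical Approach section, before unblinding, as follows.

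- Delete the p<0.05 covariate rule. Keep baseline comparisons for description only.
- State one primary analysis: linear regression of day-180 VE/VCO₂ slope on treatment, baseline VE/VCO₂ slope and PET participation (yes/no), all patients as randomised, reporting the treatment difference with its 95% CI. With baseline slope in the model, using change as the outcome gives the same treatment estimate.
- Replace the VO₂ and weight wording with VE/VCO₂ slope. In the missing-outcome sensitivity analysis, give the direction: a mean reduction in slope 10% smaller in the metformin arm and 10% larger in the placebo arm. A lower slope is the hoped-for effect, so this keeps the analysis conservative.
- Make the log model a pre-specified sensitivity analysis, run whatever the normality checks show: log day-180 slope on treatment, log baseline slope and PET participation, reported as a ratio of geometric means. It does not replace the primary model, and the log is never taken of the change.

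The cost is SAP wording and two extra model parameters in 50 patients. The baseline CPET and PET participation are already recorded, so no new data are needed. How missing day-180 values are handled is a separate matter that this change does not settle.

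### The primary regression and its missing-data sensitivity analysis are written for body weight instead of VE/VCO₂ slope, and changing the noun does not make the sensitivity analysis very conservative

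*Combined protocol and SAP*

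**What the plan says.** All of this is in the Statistical Approach section unless another place is named.

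- Primary outcome: "The primary outcome in this study will be change in VE/VCO₂ slope". The Endpoints list, the Primary Endpoint Rationale and the power paragraph agree. Body weight is secondary endpoint (f).
- Covariates that differ between arms at baseline: "we will include these variables in multivariable models of the primary endpoint as described below".
- The regression that follows: "Linear regression models will be used to regress mean weight change on treatment group using intention-to-treat principles". The documents contain no other linear regression.
- Secondary outcomes: "Analysis of secondary outcomes will be conducted using contingency tables and" Fisher's exact test, with modified Poisson regression for relative risks.
- Missing final values: "If patients are lost-to-follow up and final outcome assessments cannot be made we will use the" last observation carried forward.
- Sensitivity analysis: final values are assigned "assuming patients in the treatment group had 10% lower mean weight loss and patients in the control group had 10% greater mean weight loss". The plan comments: "This is very conservative approach that will inform the potential for differential outcomes according to follow-up status".
- Expected loss: "However, we expect very little loss-to-follow up as these patients receive regular care at our center". No figure is given.

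The CPET paragraph and Table 1 schedule exercise testing at baseline and the final visit only.

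**The concern.** Two operative steps name a variable that is not the primary endpoint. Followed literally, the section regresses weight change on treatment, tests the robustness of a weight result, and leaves VE/VCO₂ slope change with no stated model. The fault is in the plan's own wording: another variable is named in full, and nothing has been blacked out.

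A reader who mentally replaces the noun recovers the regression. The sensitivity analysis is different. Its purpose is to show whether outcomes that differ by follow-up status could explain the result. A rule that gives missing metformin patients 90% of the average metformin benefit may test very little. If such a rule is reported as very conservative, readers may place more trust in the result than the check supports.

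**Working it through.** **1. The plan's own figure.** The power paragraph gives an effect of -5, a spread of 6, 25 per arm, alpha 0.05 and 83% power. With 6 read as a standard deviation and a two-sided test, 5 / (6 × √(2/25)) = 2.946, and Φ(2.946 - 1.960) = 83.8%. The noncentral t distribution on 48 df gives 82.3%. The stated 83% is reproduced, and it is for VE/VCO₂ slope. The wrong noun therefore does not touch sample size or power. (The plan calls the 6 a variance. That is a separate matter.)

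**2. What LOCF does here.** The only CPET before the final visit is the baseline test, so the carried-forward value is the baseline slope and the imputed change is 0.

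**3. The 10% rule carried over to slope.** Let m and p be the mean changes on metformin and placebo, and f the fraction missing in each arm. Read the 10% as 10% of the arm's own mean change.

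- 10% rule: [m(1-f) + 0.9mf] - [p(1-f) + 1.1pf] = (m - p) - 0.1f(m + p)
- LOCF: (m - p)(1 - f)

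Assumptions: m = -5 and p = 0 (only their difference is in the plan), and equal numbers missing per arm. The missing counts are also assumed.

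| Missing per arm | f | 10% rule | LOCF |
|---|---|---|---|
| 1 of 25 | 0.04 | -5 + 0.5 × 0.04 = -4.98 | -5 × 0.96 = -4.80 |
| 2 of 25 | 0.08 | -5 + 0.5 × 0.08 = -4.96 | -5 × 0.92 = -4.60 |
| 5 of 25 | 0.20 | -5 + 0.5 × 0.20 = -4.90 | -5 × 0.80 = -4.00 |

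In this setting the sensitivity analysis moves the estimate by 0.5f and LOCF by 5f, a ratio of one tenth.

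**4. Where the order changes.**

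- *Unequal missingness.* Take m = -7, p = -2, with 1 metformin and 3 placebo patients missing. LOCF: -7 × 0.96 + 2 × 0.88 = -4.96. 10% rule: -7 × 0.996 + 2 × 1.012 = -4.948. With 5 placebo patients missing the figures are -5.12 and -4.932. The 10% rule is now the stricter of the two.
- *No effect.* With both arms at -2 and 5 missing in each, LOCF gives 0 and the 10% rule gives -2 × 0.98 + 2 × 1.02 = +0.08.
- *A different scale.* If 10% means 10% of the baseline slope of 32, the shift is 3.2 units in each arm. At f = 0.10 the result is -5 + 2 × 3.2 × 0.10 = -4.36, against -4.50 under LOCF.

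**5. A rising placebo slope.** With m = -3 and p = +2, 10% greater read as a multiplier gives missing placebo patients 1.1 × 2 = +2.2. That worsens placebo and so favours metformin. The direction of the rule thus depends on the sign of the placebo change.

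**6. Variance.** The rule assigns a mean-based value to each missing patient. If these are analysed as observed, the residual sum of squares comes from 25 - k patients per arm while the test uses 25 per arm and 48 df. Ignoring the 10% shift, the calculated standard error is too small by the factor √{[2(24-k)/48] × [(25-k)/25]}, which is 0.959, 0.918 and 0.796 for k = 1, 2 and 5. The nominal critical value of 2.011 then acts like 1.928, 1.846 and 1.600, for a two-sided type I error of 6.0%, 7.2% and 11.8%. Simulation of the full rule (40,000 trials, SD 6, mean change 0 in both arms, values missing completely at random) gave 6.0%, 7.2% and 11.9%, against about 5% for LOCF.

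**The case against.** The strongest reply is that the regression error is one wrong noun. The text before it points to the primary endpoint, and the section supplies the model class, the covariate rule and the intention-to-treat population. That stands, and the regression should be treated as a wording repair. A reader might infer that weight is the real primary outcome, or that the trial has no primary analysis. The documents support neither, since the endpoint is stated consistently elsewhere and the power calculation is for it.

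A reader might also infer that the regression sentence cannot refer to weight as a secondary endpoint, because secondary outcomes are sent to Fisher's test and Poisson models. That goes too far. Those methods suit binary outcomes, while weight, LVEF, BNP and peak VO₂ are continuous, so the sentence does not settle how weight is analysed. The better evidence is the promise of primary-endpoint models immediately before.

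The tempting stronger claim is that the 10% rule is always weaker than LOCF. It is not. The order depends on the size of the effect, on balanced missingness and on what the 10% is taken of, and the reversals in step 4 are plausible. Only the conditional comparison survives.

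Finally, the practical effect is small if loss is as low as the plan expects. With 1 missing per arm the two methods differ by 4.98 - 4.80 = 0.18 slope units. That also stands.

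**Conclusion.** The point holds in a limited form and should be fixed. Two operative steps name the wrong outcome, and no other place in the documents states either of them for VE/VCO₂ slope change. The intent can be inferred, and sample size and power are unaffected.

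With the noun corrected, the very conservative label is still unsupported. Under the planning effect taken as -5 and 0, equal missingness and 10% of the arm's own change, the rule shifts the estimate by 0.02 to 0.10 units where LOCF shifts it by 0.20 to 1.00. Applied literally, it also inflates type I error to about 6%, 7% and 12% with 1, 2 and 5 missing per arm. These sizes rest on assumed arm means and missing counts, and the type I figures also on no true effect and values missing completely at random. They do not show that the rule is weaker than LOCF in general. They do show that its scale, direction and variance have to be stated before anyone can say how strict it is.

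**What to change.** 1. In the regression sentence, make the dependent variable *change in VE/VCO₂ slope from baseline to day 180*, and report the treatment difference with its 95% CI.
2. Rewrite the sensitivity analysis in VE/VCO₂ slope units, with a stated scale, a direction against metformin and a valid variance. One example among several: multiply impute missing day-180 changes within arm, then add d units for metformin and subtract d for placebo, over a range of d, reporting the difference and 95% CI at each. With fraction f missing in each arm, the estimate moves by 2df. The relative shift between arms is 2d, so d = 2.5 already equals the planning effect of 5, and d = 5 would be a 10-unit relative shift. Fixed units also remove the rising-placebo problem. Delete the very conservative label, or keep it only for the upper end of the range.
3. Name VE/VCO₂ slope change in the normality sentence, and keep any check meant for VO₂.
4. Separately, as a free improvement and not part of the error: pre-specify baseline VE/VCO₂ slope and the randomisation table used (PET or non-PET) as covariates in the primary model.

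Items 1 to 3 are wording in one paragraph, and item 2 adds a short re-analysis of data already held. Item 4 uses two variables the trial already records. No new patients or visits are needed.
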